4.2 JUSTIFICATION FOR DOSE

The therapeutic play regimen for the current study (typically 25 minutes per day; 5 days per week; 4 weeks) was established based on previous work with AKL-T01 digital treatment. Specifically, a recent pivotal trial of AKL-T01 demonstrated that this regimen resulted in significant improvements in TOVA API scores in a sample of children with attention and inhibitory control deficits (STARS-ADHD).

5 STUDY POPULATION

5.1 INCLUSION CRITERIA

In order to be eligible to participate in this study, an individual must meet all of the following criteria:

1. Age 8 to 12 at the time of parental informed consent
2. Male or female
3. Confirmed ADHD diagnosis at screening/baseline visit based on DSM-V criteria and established via the MINI-KID administered by a trained clinician either in person or via teleconference
4. WISC V FSIQ ≥ 70
5. Vanderbilt ADHD Diagnostic Parent Rating Scale: Must score a 2 or 3 on at least 6 items 1-9 AND must score a 4 on at least 2, or 5 on at least 1, of items 48-54 (performance questions).
6. Consistently off stimulant medication for ≥ 1 week. OR currently on stimulant medication and agree to stop taking the medication for a 1 week prior to the baseline visit and off through duration of training and post-training assessment (note: participants will only be allowed to washout of stimulant medication if in the opinion of the investigator they are currently inadequately managed on their medication and it is appropriate to stop taking their medication for the duration of the trial)
7. Consistently off Psychotropic drug for ≥ 1 month
8. Consistently off non-stimulant medication for ADHD (e.g. atomoxetine, clonidine, guanfacine) for ≥ 1 month

9. Able to follow written and verbal instructions (English) as assessed by the PI and/or study coordinator
10. Functioning at an age-appropriate level intellectually
11. Able to comply with all testing and requirements

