1 PROTOCOL SUMMARY

1.1 SYNOPSIS

Title:	A study to assess Midline Frontal Theta (MFT) power as measured by stimulus-locked electroencephalography (EEG) before and after AKL-T01 treatment for improving attention in pediatric participants ages 8-12 years old with Attention Deficit Hyperactivity Disorder (ADHD)
Hypothesis:	ADHD children receiving 4 weeks of AKL-T01 treatment will show enhancement in MFT activity as measured by stimulus-locked EEG.
Objectives:	
Primary Objective:
 
• Demonstrate enhancement of MFT power measured by stimulus-locked EEG (Perceptual Discrimination Task (PDT)=Stimulus) in children with ADHD following 4 weeks of at-home AKL-T01 treatment. 
Secondary Objective:
 
• Demonstrate normalized MFT power in children with ADHD following 4 weeks of at-home AKL-T01 treatment. 
Exploratory Objectives:
 
• Demonstrate improvement in sustained attention by direct assessment in children with ADHD following 4 weeks of at-home AKL-T01 treatment.• Demonstrate improvement in ADHD symptoms by parent report in children with ADHD following 4 weeks of at-home AKL-T01 treatment.
Endpoints:	
Primary Endpoint:
 
• PDT-locked EEG relative to pre-training 
Secondary Endpoint:
 
• PDT-locked EEG relative to a normative control cohort 
Exploratory Endpoints:
 
• Project EVO Assessment• Test of Variables of Attention (TOVA)• Vanderbilt Assessment
Study Population:	30 children ages 8 to 12 with ADHD from the United States
Description of Study Intervention:	AKL-T01 is a digital therapeutic software for the treatment of attention and inhibitory control deficits in patients with ADHD. AKL-T01 is an investigational medical device known as Software as a Medical Device (SaMD).
Study Duration:	From beginning of enrollment to last subject last visit, 12 months
Participant Duration:	29 Days

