1.2 SCHEMA

1.3 SCHEDULE OF ACTIVITIES (SOA)

Procedures	Screening* Day -7 to -3 (Participants washing out stimulants only)	Enrollment / Baseline* Day 0	Treatment Days 1 to 27	Follow Up Day 28 +3 days
Parent Informed consent		X		
Child Assent		X		
Mini-International Neuropsychiatric Interview for Children and Adolescents (MINI-KID)		X		
Demographics	X			
Medical history	X			
Wechsler Intelligence Scale for Children V (WISC V)		X		
Ishihara Colorblindness Test		X		
Vanderbilt ADHD Diagnostic Parent Rating Scale (Initial and Follow-Up)		X		X
Social Communication Questionnaire		X		
Short Sensory Profile		X		
Social Competence Scale		X		X
Video Game Play Questionnaire		X		
Behavior Assessment for Children, Second Edition (BASC-2)		X		
Beery Visual Motor Integration (VMI)		X		
Adaptive Cognitive Evaluation (ACE) [†]		X		X
Neuroracer [†] -locked EEG		X		X
Resting State EEG		X		X
AKL-M01 (AKL-T01 Monitor) [†]		X		X
Test of Variables of Attention (TOVA) [†]		X		X
Basic Response Time (BRT)		X		X
Administer AKL-T01		X		
AKL-T01 Compliance Monitoring			X	
Adverse Event (AE) Assessment				X
Complete Case Report Forms (CRFs)	X	X	X	X

* Screening and Baseline visits may be a combined visit for participants not washing out stimulant medication.

[†] Interventions are computerized

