4 STUDY DESIGN

4.1 OVERALL DESIGN

This study is a single arm, open-label, pilot study to assess midline frontal theta (MFT) power as measured by stimulus-locked electroencephalogram (EEG) before and after treatment with AKL-T01 for improving attention in pediatric participants ages 8-12 years old with attention deficit hyperactivity disorder (ADHD).

All participants enrolled in this study will not be taking ADHD medications, including stimulants, for the duration of the study. Participants who are taking ADHD medications prior to Day 0 must have been stable off of medications for at least 30 days per parent report, or washout of medications at a Screening visit 3 – 7 days prior to Day 0.

At Baseline / Day 0, all eligible participants will complete both resting-state and PDT-locked EEG, as well as the TOVA, Vanderbilt, and AKL-M01 assessments.

All participants will then play AKL-T01 for approximately 25 minutes per day, 5 days per week, for 4 weeks at home.

At Follow-up / Day 28, participants will repeat both resting-state and PDT-locked EEG, as well as the TOVA, Vanderbilt, and AKL-M01 assessments.

All study visits for each participant should be completed during the same time of day (either AM or PM), to maintain consistent data collection and comparison of rater assessment results.

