9.2 POPULATIONS FOR ANALYSES

There will be two populations for analysis in this study.

The AKL-T01 Intervention Population will complete 28 days of AKL-T01 digital treatment. This population will enroll pediatric ADHD participants according to the inclusion criteria outlined in section 5.1 of this protocol. Only participants completing at least 50% of the prescribed treatment (i.e. 50 sessions) will be included in the analysis.

The neurotypical control group will also be analyzed as historical controls. This population was enrolled in *A pilot study to determine the feasibility of enhancing cognitive abilities in children with sensory processing dysfunction* (Anguera, 2017).

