9.3 STATISTICAL ANALYSES

All statistical analyses will be conducted using SPSS 22.0 (SPSS Inc.). Group effects for both behavioral and neural measures will be assessed with separate ANOVAs and ANCOVAs with planned follow-up contrasts (Fisher's LSD). The ANCOVA approach is considered to be a more suitable approach when post-test performance that is not conditional / predictable based on pre-test performance is the primary outcome of interest following treatment, as opposed to characterizing gains achieved from pre-training performance (for example, group X session interaction(s)). However, both are appropriate statistical approaches that have been used to assess cognitive training outcomes. Thus, our approach will be to present the p-values for each approach. Planned follow-up contrasts will be used to directly assess changes within each group. To minimize influential data points, we will remove values +/- 2 standard deviations for all group analyses. For correlations tested, we will use a more stringent outlier removal procedure (Cook's D> 1) given the smaller cohort size and possible inflated change scores.

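### The Day 0 Vanderbilt is both entry threshold and baseline, so a single-arm fall in parent-rated symptoms cannot by itself demonstrate improvement (exploratory objective; minor)

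*Combined protocol and SAP*

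**What the plan says.** **Entry.** Criterion 5 in Section 5.1 sets two thresholds on the parent's rating: "Must score a 2 or 3 on at least 6 items 1-9 AND must score a 4 on at least 2" of items 48-54, with a single 5 on those items as the alternative to two 4s. All inclusion criteria must be met, so the MINI-KID diagnosis in criterion 3 adds to the Vanderbilt threshold and does not replace it.

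**Timing.** In the Schedule of Activities (Section 1.3), the row that begins "Vanderbilt ADHD Diagnostic Parent Rating Scale (Initial and Follow-Up" is marked at Day 0 and Day 28 only. Nothing is marked at Screening, and the footnote adds: "Screening and Baseline visits may be a combined visit for participants not washing out stimulant medication". Section 4.1 has the scale completed at Day 0 and says that at Day 28 "participants will repeat both resting-state and PDT-locked EEG, as well as the TOVA, Vanderbilt, and AKL-M01 assessments".

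**Use.** The synopsis (Section 1.1) names the Vanderbilt as an exploratory endpoint, with the objective: "Demonstrate improvement in ADHD symptoms by parent report in children with ADHD following 4 weeks of at-home AKL-T01 treatment". Section 8.1 files it under efficacy. The exploratory row of Section 3 lists only reaction-time measures and no parent report.

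**Comparison.** Section 4.1: "This study is a single arm, open-label, pilot study". Section 9.2: "The neurotypical control group will also be analyzed as historical controls". Section 9.3: "Planned follow-up contrasts will be used to directly assess changes within each group". Section 9.3 mentions neither a second pre-treatment rating nor regression to the mean.

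**The concern.** A parent rating varies from one occasion to the next. A threshold on a single rating keeps children whose score happened to be high that day and turns away those whose score happened to be low. If that same rating is the baseline, the mean at Day 28 is expected to be lower even if nothing has changed.

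A concurrent control group selected in the same way would show the same fall, and the comparison would cancel it. This study has no such group. The historical neurotypical children were enrolled in another study and were not admitted under criterion 5, so their change does not estimate the fall. Adjusting for baseline by ANCOVA does not supply the missing untreated ADHD group either.

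What is at stake is the word *demonstrate* in one exploratory objective. Section 2.3.2 already names parent-reported inattention as a potential benefit, so a significant fall could be read as confirming it.

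**Working it through.** The documents give no sample size calculation, alpha, SD, retest correlation or pass rate, so there is no figure of the plan's own to reproduce. The check asks how large the artefact would be with no treatment effect.

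**Inputs from the documents.** 30 children (synopsis); selection on the Day 0 rating (criterion 5 and the Schedule); within-group change from Day 0 to Day 28 (Sections 4.1 and 9.3).

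**Assumptions.** Scores are normal in the assessed children. The retest correlation r is 0.7 to 0.9. A share q of the assessed children passes the threshold. The test is a paired t test at two-sided 5%, counting only significance toward improvement (nominal 2.5%).

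**Formulas.** With threshold c = Φ⁻¹(1 − q) in SD units and λ = φ(c)/q:
- expected fall = (1 − r)λ;
- variance of the baseline among those admitted, v = 1 + cλ − λ²;
- SD of change = √[(1 − r)²v + 1 − r²].

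**Worked case, q = 80%, r = 0.7.** c = −0.842 and λ = 0.280/0.80 = 0.350. The expected fall is 0.3 × 0.350 = 0.105 SD. v = 1 − 0.295 − 0.123 = 0.583 before rounding of the terms, and the SD of change is √(0.09 × 0.583 + 0.51) = 0.750. The fall divided by its standard error is 0.105/(0.750/√30) = 0.77. Simulation of 20,000 trials gives significant improvement in 11.1%.

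**Results for 30 children, no effect, r from 0.9 to 0.7:**

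| Share passing | Expected fall (SD) | Falsely significant improvement |
|---|---|---|
| 95% | 0.011 to 0.033 | 3.5% to 4.0% |
| 80% | 0.035 to 0.105 | 6.0% to 11.1% |
| 65% | 0.057 to 0.171 | 10.5% to 22.4% |
| 50% | 0.080 to 0.239 | 16.1% to 40.2% |
| 31% (c = +0.5 SD) | 0.11 to 0.34 | 28% to 70% |
| 16% (c = +1 SD) | 0.15 to 0.46 | 45% to 92% |

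If only 24 children are analysed (an assumed figure, since Section 9.2 drops those below half of the prescribed treatment), the expected fall is unchanged. The error rates become 3.3% to 3.9%, 5.4% to 9.6% and 13.2% to 32.9% for 95%, 80% and 50% passing.

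**Check with the actual form of the rule.** A second simulation used nine items scored 0-3 and admitted children with at least six items scored 2 or 3. With r of about 0.7 to 0.9, the fall on the 27-point total and the false-improvement rate were:
- 84% passing: 0.19 to 0.53 points, 6% to 11%;
- 70% passing: 0.34 to 0.97 points, 10% to 22%;
- 56% passing: 0.47 to 1.35 points, 14% to 36%.

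The rule on items 48-54 was not modelled. When a separate later rating served as baseline in the same simulation, with errors independent between occasions, the mean change was within 0.01 points of zero and the error rate 2.3% to 2.7%. The double use of one rating is therefore the source of the fall in these models.

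**The case against.** The strongest reply is that the effect may be negligible. Every child must also have clinician-confirmed ADHD, so most of those assessed may pass criterion 5. A 50% pass rate means assessing 30/0.50 = 60 children on this criterion alone, and a 16% pass rate about 30/0.159 = 189. Nothing in the documents points to screening on that scale. At 95% passing, the error rate is barely above nominal. This stands as a limit on size. It does not remove the bias, which always runs toward improvement and which nothing in the plan estimates.

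A second reply is that this is one exploratory objective in a pilot and that Section 3 lists no parent-report endpoint. That also stands, and it is why the point is minor. The synopsis wording still claims more than the design can deliver.

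A reader might also infer that parents inflate the Day 0 rating because they know the child must qualify. The documents support only that the study is open label. They do not say what parents know about the threshold.

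Finally, a reader might think the remedy is to take the qualifying rating at the Screening visit. Section 4.1 starts washout at that visit, so the rating could reflect medicated behaviour while other children qualify off medication. The Schedule marks consent and assent only at Day 0. Children with a combined visit would keep the same problem, which would leave two kinds of baseline.

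**Conclusion.** The point holds as a minor one. As planned, the change in the Vanderbilt from Day 0 to Day 28 is biased toward improvement by selection on its own baseline, and the within-group change cannot by itself demonstrate improvement. The size runs from 0.01-0.03 SD with 3-4% false significance (95% passing) to 0.08-0.24 SD with 16-40% (50% passing), and more under stricter thresholds. These figures rest on assumed normality, on r between 0.7 and 0.9, and on pass rates that the documents do not give. The documents also do not say which Vanderbilt score is the endpoint.

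Two stronger readings are not supported. One is that a significant fall is the expected result without any effect. In the table above, false significance passes 50% only when fewer than half of the assessed children pass, and then only at the lower correlations. The other is that the trial's main conclusions are compromised. The primary and secondary endpoints are EEG measures, children are not selected on them, and they are not directly affected.

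Removing the selection artefact would not settle the parent-report question either. Parental expectancy in an open-label study and natural change over four weeks would remain, and those need a concurrent control.

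**What to change.** 1. In the synopsis, replace the objective of demonstrating improvement by parent report with: *Describe change in parent-reported ADHD symptoms.*
2. In Section 9.3, add: *Change on Vanderbilt items 1-9 and 48-54 includes regression to the mean, because eligibility was set on the same Day 0 rating, and is not evidence of improvement on its own.*
3. Optionally, if the follow-up form carries them, report change on items not used for selection next to change on the selected items. This is a partial check only, because one parent's rating error may be shared across items.
4. While editing, reconcile the synopsis with Section 3 on whether the Vanderbilt is an exploratory endpoint, and name the score to be analysed.

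No new visit or form is needed. The cost is a few lines of text, at most one extra analysis line, and a weaker claim on one exploratory endpoint. Reporting how many assessed children failed criterion 5 would let readers place the result in the table above.

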5.2 EXCLUSION CRITERIA

An individual who meets any of the following criteria will be excluded from participation in this study:

1. Current controlled (requiring a restricted medication) or uncontrolled, comorbid psychiatric diagnosis, based on the Neurodevelopment Intake Form, BASC, and subsequent clinical interviewing, with significant symptoms including but not limited to post-traumatic stress disorder, psychosis, bipolar illness, severe obsessive compulsive disorder, severe depressive or anxiety disorder, conduct disorder, or other symptomatic manifestations that in the opinion of the Investigator may confound study data/assessments. (Participants with clinical history of learning disorders will be allowed to participate as long as the disorder does not impact their ability to participate based on PI judgement).
2. Autism Spectrum Disorder concern as indicated from the Social Communication Questionnaire ≥ 15 .
3. Current treatment with stimulant treatment for ADHD and unwilling or inappropriate (per investigator opinion) to washout.
4. Initiation or completion of behavioral therapy within the last 4 weeks. The participant should inform the Investigator if they intend to change their behavioral therapy during the 4 weeks of the study. Participants who have been in behavior therapy consistently for more than 4 weeks may participate if their routine is unchanged throughout the study.
5. Participant is currently considered at risk for attempting suicide by the Investigator, has previously made a suicide attempt, or has a prior history of, or is currently demonstrating active suicidal ideation or self-injurious behavior, as measured by MINI-KID Suicidality Module C.
6. Motor condition (e.g. physical deformity of the hands/arms) that prevents game playing as reported by the parent or observed by the Investigator.
7. Recent history or suspicion (within the past 6 months) of substance abuse or dependence.
8. History of seizures (excluding febrile seizures).
9. Participation in a clinical trial within 90 days prior to screening.
10. Color blindness as detected by Ishihara Color Blindness Test.
11. Regular use of psychoactive drugs that in the opinion of the Investigator may confound study data/assessments.
12. Any other medical condition that in the opinion of the Investigator may confound study data/assessments.
13. Previously received AKL-T01 (Project-EVO™) treatment in a previous clinical trial.

6 STUDY INTERVENTION

6.1 STUDY INTERVENTION

6.1.1 STUDY INTERVENTION DESCRIPTION

AKL-T01 digital treatment is a state-of-the-art mobile video game-like platform, which deploys modern videogame graphics, engaging reward loops, and real-time adaptive mechanics to dynamically personalize difficulty based on the user's ability. AKL-T01 multitasking treatment employs perceptual discrimination attention/memory task as well as a continuous motor "driving" task. Performance on these tasks are assessed in isolation and when performed together to calculate a performance index for each individual user. A personalized multitask treatment regimen is automatically configured and delivered to the user and is optimized adaptively to increase multitask performance. As players proceed through the treatment periodic recalibration occurs to maintain an optimal difficulty level.

6.1.2 STUDY INTERVENTION COMPLIANCE

AKL-T01 automatically captures gameplay compliance and uploads these data directly to a central server when connected to WiFi. The server will automatically push daily compliance emails to the research coordinator. Based on these emails study staff can then reach out to parents and caregivers of participants to trouble shoot technical problems and/or encourage more play.

Additionally, AKL-T01 contains built-in features that remind the participant to play each day.

6.2 CONCOMITANT MEDICATION AND TREATMENT

With the exception of common over the counter (OTC) (e.g. ibuprofen, acetaminophen, non-sedating antihistamines to treat seasonal allergies) and prescription medications (e.g. antibiotics) for minor transient ailments, regular use of concomitant medications are not permitted during the study.

Concomitant medications and treatment are as follow:

1. Psychotropic medication
2. Stimulant medication
3. Non-stimulant medication for treatment of ADHD (e.g. atomoxetine, clonidine, guanfacine)

Transient use of some non-sedating antihistamines is allowed.

Study Investigators can approve short-term use of other medications that are not anticipated to confound study assessments.

7 STUDY INTERVENTION DISCONTINUATION AND PARTICIPANT DISCONTINUATION/WITHDRAWAL

7.1 DISCONTINUATION OF STUDY INTERVENTION

AKL-T01 study intervention may be discontinued by the participant or investigator at any time during the study.

7.1.1 PARTICIPANT DISCONTINUATION OR WITHDRAWAL

Participants are free to withdraw from participation in the study at any time upon request without prejudice.

An investigator may discontinue or withdraw a participant from the study for the following reasons:

- Disease progression which requires discontinuation of the study intervention
- If the participant meets an exclusion criterion (either newly developed or not previously recognized) that precludes further study participation
- Participant unable to receive AKL-T01 for 5 days/weeks as prescribed per protocol
- If any clinical adverse event (AE) or other medical condition or situation occurs such that continued participation in the study would not be in the best interest of the participant

The investigator or designee will notify the sponsor or their designee immediately when a subject has been discontinued or withdrawn from study treatment because of an adverse experience. Any adverse experiences that are present at the time of discontinuation/withdrawal should be reported and followed up in accordance with the safety requirements outlined in Section 8.3 (Adverse Events).

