7.1.2 LOST TO FOLLOW-UP

A participant will be considered lost to follow-up if he or she fails to return for Day 28 Exit visit and is unable to be contacted by the study site staff.

The following actions must be taken if a participant fails to return to the clinic for a required study visit:

- The site will attempt to contact the participant and reschedule the missed Follow-up / Day 28 visit.
- Before a participant is deemed lost to follow-up, the investigator or designee will make every effort to regain contact with the participant.
- Should the participant continue to be unreachable, he or she will be considered to have withdrawn from the study with a primary reason of lost to follow-up.

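### Section 7.1.1 permits study withdrawal of a child who cannot use AKL-T01 5 days a week, so a child whom the 50% rule would include can miss the only post-treatment EEG (minor)

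*Combined protocol and SAP*

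**What the plan says.** Section 7.1 treats stopping the device as a separate act: "AKL-T01 study intervention may be discontinued by the participant or investigator at any time during the study". Section 7.1.1 goes further. Its lead-in is "An investigator may discontinue or withdraw a participant from the study for the following reasons", and one listed reason is "Participant unable to receive AKL-T01 for 5 days/weeks as prescribed per protocol" (read here as 5 days per week, in line with 4.1). The closing paragraph of 7.1.1 uses a different level, referring to the time "when a subject has been discontinued or withdrawn from study treatment because of an adverse experience". The only follow-up it describes is for adverse experiences.

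Section 7.1.2 has a retention step, "The site will attempt to contact the participant and reschedule the missed Follow-up / Day 28 visit", but it is for a child who fails to come back. The Schedule of Activities (1.3) has no early-termination visit and marks the task-locked EEG at Baseline and Follow Up only.

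On dose, 4.1 says "All participants will then play AKL-T01 for approximately 25 minutes per day, 5 days per week, for 4 weeks at home". On measurement, it says "At Follow-up / Day 28, participants will repeat both resting-state and PDT-locked EEG". On who is analysed, 9.2 says "Only participants completing at least 50% of the prescribed treatment (i.e. 50 sessions) will be included in the analysis". Section 9 has no rule for a missing Day 28 value.

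**The concern.** Two adherence standards meet at one visit. Section 9.2 accepts a child from half of treatment upward. Section 7.1.1 makes falling short of the full weekly schedule a possible reason to leave the study. A child between the two standards can be one whom the analysis would include and yet one whom the investigator has withdrawn.

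The primary endpoint in section 3 is a change in MFT power, so a child without a Day 28 EEG contributes nothing to it. The study has one arm and is open-label, so there is no control group in which similar withdrawals might offset. If inability to keep the schedule is unrelated to MFT change (a technical fault, say), only precision is lost. If it goes with a poorer change, the remaining mean is biased upward. An EEG that was never recorded cannot be restored by a later sensitivity analysis, so the matter has to be settled in the protocol.

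**Working it through.** **1. The plan's own figure.** There is no sample-size calculation, alpha, SD or dropout rate to reproduce. The one relevant figure is the 50 sessions in 9.2.

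- Prescribed total: 50 / 0.50 = 100 sessions.
- Play days from 4.1: 5 × 4 = 20.
- Sessions per play day: 100 / 20 = 5. The documents do not state this. It fits the 20-day regimen but is an inference.

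**2. Who falls between the two rules.** At 5 sessions per play day over 4 weeks:

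| Pattern | Sessions if continued to Day 28 | Meets 50%? | Reaches 50 sessions after |
|---|---|---|---|
| 5 days/week | 100 | yes | 10 play days (2 weeks) |
| 4 days/week | 80 | yes | 50/20 = 2.5 weeks |
| 3 days/week | 60 | yes | 50/15 = 3.3 weeks |
| 2 days/week | 40 | no | not reached |

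A child limited to 3 or 4 days a week can be read as fitting the 7.1.1 reason. There are two ways to lose such a child:

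- Withdrawal after session 50. The child already meets 9.2 but has no Day 28 EEG. The window is the last 4 − 2.5 = 1.5 weeks at 4 days a week, or the last 4 − 3.3 = 0.7 weeks at 3 days a week.
- Withdrawal before session 50. The child would have met 9.2 by continuing, but neither reaches the threshold nor has the EEG.

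A child at 2 days a week fails 9.2 in any case and is outside this point.

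**3. Possible bias.** Every input except n = 30 is an assumption. 100,000 simulated trials were run with no true change and a latent adherence score correlated r with MFT change. Section 9.2 removes the lowest k0 children on that score, and 7.1.1 then removes the next-lowest 1, 2 or 3. The ±2 SD removal in 9.3 is applied once, to change scores. The table gives the shift in the mean that 7.1.1 adds, in SD of change, for 1 / 2 / 3 children.

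| r | k0 = 3 | k0 = 0 |
|---|---|---|
| 0.1 | 0.005 / 0.010 / 0.015 | 0.007 / 0.013 / 0.019 |
| 0.3 | 0.016 / 0.031 / 0.046 | 0.021 / 0.038 / 0.055 |
| 0.5 | 0.026 / 0.051 / 0.076 | 0.032 / 0.061 / 0.088 |

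At r = 0 the shift is zero within simulation error. Removing strictly the next-lowest children is an upper-end assumption. Without the ±2 SD step, k0 = 3 with 3 further children gives 0.015, 0.046 and 0.076, so that step hardly matters here.

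For scale, the standard error of a mean change at n = 30 is 1/√30 = 0.18 SD. The largest entry is 0.088 / 0.183 = 0.48 of a standard error.

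**4. Precision without bias.** The standard error rises by √(30/29) = 1.017, √(30/28) = 1.035 or √(30/27) = 1.054, that is, by 1.7, 3.5 or 5.4%.

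**The case against.** The strongest answer is that the protocol, read as a whole, keeps partly adherent children. Section 6.1.2 meets low play with daily compliance emails, troubleshooting and encouragement. Section 9.2 admits children from 50%, which presupposes that they reach Day 28. Section 4.1 has participants repeat the EEG, and 7.1 allows the device alone to be stopped. The 7.1.1 clause speaks of being unable to receive the device, which is narrower than playing on fewer days, and it is permissive. Much of this stands: the default is probably retention, and the gap opens only if the discretion is used. It does not close the gap, because 7.1.1 names the study as what the child leaves, and no other section brings a withdrawn child back for Day 28.

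A second answer is that children who finish with 60 or 80 sessions were, by definition, not withdrawn. That is right. The children at risk are those withdrawn on the way there.

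A third is that this is a 30-child mechanism pilot with an exposure-based analysis set, and 9.2 describes its population as completing 28 days of treatment. Restricting analysis to treated children is a legitimate choice, and 9.2 may well select more than 7.1.1 does. But that supports letting 9.2 alone decide inclusion.

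A reader might infer that the protocol requires partial adherers to be removed, or that it makes 5 days a week the real inclusion standard. The text supports neither.

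**Conclusion.** The gap is real, and its severity is minor. A discretionary ground for leaving the study sits above the 50% bar for analysis, with nothing to secure the Day 28 EEG for a child withdrawn under it. The text alone establishes this. The example patterns rest on the inferred 5 sessions per play day.

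The size is not known, because the documents give neither a withdrawal rate nor a correlation between adherence and MFT change. For 1 to 3 of 30 children the illustrative cost is a shift of 0.005 to 0.088 SD when r is 0.1 to 0.5, and a 1.7 to 5.4% larger standard error. The added shift is zero if r = 0, or if the same children would fail 9.2 anyway.

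A reader might infer that the primary result will be materially inflated. The documents do not support that. The decision to withdraw comes before the Day 28 EEG, so it cannot select on the observed outcome. Even the extreme scenario stays under half a standard error. Nor is the disease-progression ground in 7.1.1 a fault: 4.1 and 6.2 bar ADHD medication during the study, so leaving the study in that case is defensible.

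**What to change.** In 7.1.1:

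- Delete inability to receive AKL-T01 5 days a week as a ground for withdrawal from the study.
- State that a partly adherent child may continue AKL-T01 at the rate the child can manage. Turning the clause into a ground for stopping the device would not be enough, because it could push a child heading for 60 or 80 sessions below 50 and so out of the 9.2 set.
- State that any child who plays less or stops the device is still asked to attend Day 28 (PDT-locked EEG, TOVA, Vanderbilt), unless consent or assent is withdrawn or attendance is against the child's interest.
- Use the terms for the study and for study treatment consistently.

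On the case report form, record the device-stop date and any ADHD medication restarted before Day 28. Show the primary result with and without EEGs taken after either event. The 50% rule in 9.2 then alone decides inclusion in the main analysis, and children below it stay out unless 9.2 is also changed.

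The cost is a wording amendment, two form fields and a visit that is already scheduled. The downsides are one more attendance for a few children, some EEGs possibly confounded by restarted medication, and a possibly less favourable mean change.
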